7. SUMMARY OF BASELINE INFORMATION

7.1. Subject Accountability

A summary table will provide the total number of subjects screened, enrolled, and who have completed the clinical trial. The subjects eligible for this study and compliant with each follow-up contact will be summarized descriptively. Subjects withdrawn from study, lost follow-up, and lost with other reasons will be tabulated together with their reasons.

7.2. Demographics and Baseline Characteristics

The baseline characteristics and demographics of each study subject will be collected during the subject screening process. For subject demographics such as age, sex, race, ethnicity, and other demographic variables will be used for each summary. All measurements will be presented using descriptive statistics; continuous variables, such as age, body height, body weight, body mass index, will be summarized as described in section 6.1.

 Edwards	Revision Date: May 7, 2024	Rev	For Use Only by Affiliates of Edwards Lifesciences	Page 14
	Title	A randomized trial of the Hypotension Prediction Index in the cardiac operating room and the intensive care unit		

The CONSORT (Consolidated Standards of Reporting Trials) Flow Diagram will be drawn to represent study subjects count and its percentage dynamics from subject qualification screening, eligible subject enrollment, and intervention (randomization) allocation, follow-up, and data analysis.

7.3. Medical History

Patient's medical historical data will be recorded with electronic case report form (eCRF). Medical historical data will be summarized into tables with continuous variables being represented by mean, stand deviation, median, and ranges, and categorical variables being represented by counts and percentages.

7.4. Procedural Information

Procedure data including the surgery classification, planned surgical technique, duration, and procedural interventions will be summarized.

8. STATISTICAL ANALYSIS OF STUDY ENDPOINTS

8.1. Primary Effectiveness Endpoint

Primary objective of this clinical study is to determine whether the use of the Acumen™ HPI Feature Software to guide hemodynamic management in patients undergoing cardiac surgery requiring cardiopulmonary bypass reduces the mean duration of hypotension (defined as MAP < 65 mmHg) from the post-bypass period in the cardiac operation room (OR) and the cardiovascular intensive care unit (CVICU). With MAP measurements sampled during post-CPB and up to first 8 hour in ICU, downloaded from the advanced hemodynamic monitoring platform, the primary effectiveness endpoint the hypotension duration of study subject is calculated with the algorithm illustrated in sample size estimation section 2.4.3.

The primary effectiveness endpoint will be analyzed on the FAS population.

8.1.1. Summary Statistics and Statistical Comparison

The computed total hypotension duration of study subject allocation in the HPI arm and control group will be summarized using descriptive statistics including mean, median, minimum, maximum, standard deviation, Q1 (first quantile), and Q3 (third quantile), and present these descriptive statistics by study arms in the summary table. Additionally, the p-value from a two sample mean t-test will be provided to test the difference.

8.1.2. Primary Effectiveness Endpoint Analysis

We will test the following hypothesis:

$$\begin{aligned} H_n: \mu_{HPI} &\geq \mu_{ctr} \\ H_a: \mu_{HPI} &< \mu_{ctr} \end{aligned}$$

Here μ_{HPI} , μ_{ctr} are the mean number of minutes of hypotension duration of HPI arm study subjects and that of control group study subjects respectively.

A two-sample t-test will be used to judge if the hypotension duration of HPI arm is statistically shorter or smaller than the outcomes of control group without HPI software. We will use the following:

$$t = \frac{\hat{\mu}_1 - \hat{\mu}_0}{\sqrt{S_p^2 \left(\frac{1}{n_1} + \frac{1}{n_0} \right)}}$$

 Edwards	Revision Date: May 7, 2024	Rev	For Use Only by Affiliates of Edwards Lifesciences	Page 15
	Title	A randomized trial of the Hypotension Prediction Index in the cardiac operating room and the intensive care unit		

Here $\widehat{\mu}_1$, $\widehat{\mu}_0$ are the mean hypotension duration estimation of HPI arm and control group, respectively, the pooled variance $S_p^2 = \frac{(n_1-1)*S_1^2 + (n_0-1)*S_0^2}{n_1+n_0-2}$, n_1, n_0 is the final valid subjects in HPI arm and control group respectively, S_1^2, S_0^2 is the variance estimates of HPI arm, and control group respectively.

By the t statistics calculated with the data collected during clinical operation, compares to the critical t value ($t(\alpha', n_1 + n_0 - 2)$) to judge if null hypothesis is rejected. Here α' is the split type I error by study design for interim analysis and the final analysis, $n_1 + n_0 - 2$ is the degree of freedom.

For the interim analysis, by Pocock methodology [15-16] with one-sided t test, $\alpha' = 0.0154$. If $\widehat{\mu}_1 - \widehat{\mu}_0$ is negative, and the actual p value calculated from the t statistics based on designed null hypothesis from the trial outcomes is less than α' , H_{null} will be rejected. Following conclusion will be drawn: the application HPI software system in hemodynamic management statistically reduces the hypotension duration in HPI arm.

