On the day of the procedure, the subject will be randomized into the HPI arm or the non-HPI arm (control group). If the subject is randomized into the HPI arm, the clinician will receive trial research nurse support and will use the Acumen™ HPI Software Feature with the Acumen IQ Sensor to monitor the subject. The initiation of HPI in the CVICU will not start until 15-30 minutes after the HPI arm subject arrives in the CVICU. Once HPI is initiated in the CVICU, HPI-based interventions will be held for at least 5 minutes before extubation and will also be held for at least another 5 minutes after extubation.

All subjects, regardless of randomization, will be equipped with an Acumen IQ Sensor. If the subject is not randomized into the HPI arm, the clinician will use non-protocolized standard of care.

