2.4.3. Sample Size Estimate

Because there is no valid evidence available for the hemodynamic management from literature on intensive care unit, in this simulation only the information from closed chest stage and post cardiac pulmonary bypass stage are integrated.

By HPI CARE study objectives, clinical study design, and hypotheses test settings, a one side hypothesis test is the standard method, type I error for this test is 0.025, test power=0.80, control group mean hypotension duration=29 minutes, its stand deviation=29.49, the expected reduction is 30%, by the HPI arm result from non-cardiac clinical study, the ratio between hypotension duration STD and mean is around 1.10. The estimated subjects for each arm by 1:1 allocation is 142 from the simulation completed by SAS PROC POWER. Considered lost follow up, withdraw informed consent form, et al, 10% attrition will put on the estimated sample size. It is 157 subjects for HPI arm and control group.

Variable	Control Group (non-HPI arm)	Test Group (HPI Arm)
----------	--------------------------------	-------------------------

 Edwards	Revision Date: May 7, 2024	Rev	For Use Only by Affiliates of Edwards Lifesciences	Page 9
	Title	A randomized trial of the Hypotension Prediction Index in the cardiac operating room and the intensive care unit		

Mean hypo (minutes)	29 min	20.3 min
SD of Mean hypo minutes	29.49 min	22.33 min
Alpha (overall, one-sided)	0.025	---
Sides	One-Sided	---
Power	0.8	---
Sample size	142	142
Dropout rate	10%	10%
Sample size (subjects)	157	157

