5.1. Analysis Dates and Days

Reference Start Date (Day 0)

On the day of the surgery, the start of the study is defined as when the arterial line has been connected and after initial stabilization (max 15 minutes). The date of the surgery will be used as the reference start date (day 0).

If a subject has multiple procedure forms, we will present information on the procedure with the earliest date where the site has indicated that the arterial line was placed.

If no form has this indicated, then the procedure information corresponding to the procedure with the earliest date that indicated an arterial line was placed will be used. If no form has this listed, then the date of the earliest procedure will be used.

Last Participation Date

The Last Participation Date is defined as the last date recorded. This will be the study exit date if the subject has exited the study or the latest date the subject was known to be alive and on study.

Treatment Start Date

The Treatment Start Date is defined as the date of the surgery.

Study Day

Study Day = Date – Reference Start Date

Last Participation Day

Last Participation Day = Last Participation Date – Reference Start Date

Note: Last Participation Day is used as the censor day for any survival analysis.

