8.6. Exploratory Analyses

The following exploratory analyses will be performed. These analyses will be presented for the FAS population.

- Protocol adherence to HPI alert, as defined by >50% HPI alerts with documented intervention per the suggested treatment algorithm within a 5-minute timeframe

 Edwards	Revision Date: May 7, 2024	Rev	For Use Only by Affiliates of Edwards Lifesciences	Page 18
	Title	A randomized trial of the Hypotension Prediction Index in the cardiac operating room and the intensive care unit		

For each subject, it is likely that there will be several decisions necessary. Each decision will be made separately, and the overall rate of compliance will be calculated.

A full definition of the compliance algorithm, can be found in section 12.2.

- Difference in time spent in hypertension defined as TWA of MAP>110, >120 and >130 mmHg post-cardiopulmonary bypass CPB) through the first 8-hour ICU period as compared with the control group. The time spent in hypertension will be calculated in a similar manner to the primary endpoint. The only difference will be that we are looking for the amount of time above the hypertension thresholds instead of below it. The average time will be calculated by arm and the difference will also be presented.
- In-hospital mortality rate
The mortality rate will be calculated as a simple proportion for each arm and for the difference between the two arms.
 - Incidence of cerebral desaturations defined as total time below 10% relative to baseline NIRS values. For each subject, the baseline NIRS value will be established at The time below 10%
- Percent of monitoring time with CO or CI within 10% relative to pre-induction baseline
The baseline CO and CI will be calculated pre-induction. The percent of the monitoring time within 10% of the baseline value will be calculated and presented by and for the difference between the arms.
- Hospital Length of Stay (days)
The hospital length of stay will be calculated starting with the procedure time until the subject is discharged. LoS will be calculated and presented by and for the difference between the arms.
- ICU Length of Stay (hours)
- Time to extubation (hours)
The time to extubation will be calculated as the amount of time from intubation until extubation. The average time will be presented by arm and the difference will also be presented.
- New onset atrial fibrillation, detected prior to ICU discharge

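### The primary t-test uses no baseline covariates, and no adjusted analysis is planned, although suitable baseline values are collected: a missed efficiency of unknown size, not an error

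*Combined protocol and SAP*

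**What the plan says.** SAP 8.1.2 states: "A two-sample t-test will be used to judge if the hypotension duration of HPI arm is statistically shorter or smaller". The statistic is the difference in arm means over a pooled standard error. Protocol section 7 gives the same formula. Neither contains a covariate.

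SAP 8.1.3 varies the MAP threshold and the minimum episode length, resamples the data, and adds back subjects with missing covariate information. That last item presupposes covariates, but no model using any is defined.

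SAP 2.3 describes randomization in blocks of 2, 4 or 6 with no stratification factor.

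Baseline data are collected all the same. SAP 7.2 lists age, sex, race, height, weight and BMI. Protocol section 4 (Schema) calls for baseline creatinine, NT pro-BNP and troponin on the day of the procedure. SAP 7.4 lists surgery classification and planned technique, under procedural information.

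On monitoring, protocol section 6 says: "All subjects, regardless of randomization, will be equipped with an Acumen IQ Sensor". SAP 8.6 says: "The baseline CO and CI will be calculated pre-induction".

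**The concern.** If a baseline variable predicts minutes of hypotension, leaving it out of the analysis leaves its variance in the standard error. Including it narrows the interval and raises power at the same sample size, while the target stays the difference in mean minutes. It also reduces the effect of chance imbalance in the covariates modelled, and nothing in an unstratified design otherwise does so. Eligible operations are mixed (CABG, valve or a combination), so some spread in prognosis is plausible.

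The question matters here because planned power is close to its 80% target once the interim look and attrition are counted. A modest gain in precision would supply a margin that the design otherwise lacks.

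**Working it through.** **Inputs (SAP 2.4.3).** Control mean 29 min, SD 29.49. HPI mean 29 × 0.70 = 20.3 min, SD 1.10 × 20.3 = 22.33. Difference 8.7 min. Error rates: "type I error for this test is 0.025, test power=0.80", one-sided.

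**The plan's own figure.** n per arm = (1.960 + 0.842)² × (29.49² + 22.33²) / 8.7² = 7.849 × 1368.29 / 75.69 = 141.9, so 142. This matches the SAP.

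**Evaluable subjects.** SAP 8.1.4 plans 175 per group with 10% attrition: 175 × 0.90 = 157.5 per arm. (Going forward, 142 × 1.11 / 0.90 = 175.1.)

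**Power with the interim look.** Assume the interim falls at half the information and that the SAP's one-sided 0.0154 applies at both looks, so the critical z is 2.160. The two z-statistics have correlation √0.5. Under adjustment,

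SE = √[1368.29 × (1 − R²) / 157.5], final drift = 8.7 / SE, interim drift = final drift × √0.5.

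Unadjusted: SE = 2.947 min, drifts 2.087 and 2.952, power 80.5%.

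**R² is an assumption.** The documents relate no baseline value to hypotension minutes. Over a range:

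| R² | SE (min) | Power | 95% CI half-width (min) | Equivalent extra subjects per arm |
|---|---|---|---|---|
| 0 | 2.947 | 80.5% | 5.78 | 0 |
| 0.02 | 2.918 | 81.3% | 5.72 | 3 |
| 0.05 | 2.873 | 82.5% | 5.63 | 8 |
| 0.10 | 2.796 | 84.5% | 5.48 | 17 |
| 0.20 | 2.636 | 88.5% | 5.17 | 39 |

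The half-width is 1.96 × SE, ignoring the interim. The last column is 157.5 / (1 − R²) − 157.5, rounded down.

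**Cost if the covariates predict nothing.** With three useless covariates and 315 subjects, the variance rises by a factor of about 1 + 3 / (315 − 6) = 1.010. Power falls from 80.5% to about 80.1%.

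**Dependence on the nominal level.** At 0.0147 per look, which holds the overall one-sided error at 0.025 for two equally spaced looks, the powers for the five rows are 80.0%, 80.8%, 82.0%, 84.1% and 88.2%. The increments hardly change.

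**The case against.** The t-test is valid under randomization. It matches the stated hypotheses, the protocol formula and the sample-size basis, and it estimates the intended mean difference. That stands in full.

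Four stronger readings are tempting, and the documents do not support them:

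- *Pre-induction MAP is already a recorded baseline that the analysis ignores.* Readable current text defines a pre-induction baseline for CO and CI only. MAP is named in the Revision C change summary, as an and/or option, and a change log is not current plan text. SAP 5.1 says "the start of the study is defined as when the arterial line has been connected and after initial stabilization", which does not place recording before induction. Since both arms carry the sensor and CO/CI is to be derived before induction, MAP is probably recoverable, but that is an inference.
- *Surgery classification is a baseline value.* SAP 7.4 lists it beside duration and procedural interventions. If it records the operation performed, it arises after randomization.
- *Precision is certainly being lost.* At R² of 0.02 the gain is under one point. SAP 2.4.3 also says the planning inputs contain no ICU evidence, although the endpoint includes eight ICU hours, so the base power and every increment are notional.
- *The change is free up to database lock.* With an effectiveness interim planned, covariates chosen after an unblinded look could be chosen on the results.

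These points narrow the claim. They leave the asymmetry: a possible gain of several points against a cost of a fraction of one.

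**Conclusion.** The point holds as a missed efficiency. The primary test is unadjusted, no adjusted analysis is planned in any role, randomization is unstratified, and usable baseline values are collected. The result of the planned test would not be invalid.

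The size is conditional. Against 80.5% unadjusted, the gain runs from about 0.8 of a point at R² = 0.02 to 8 points at R² = 0.20, and the documents do not say where in that range the trial lies. The figures rest on the SAP's means and SDs, 157.5 evaluable subjects per arm, an interim at half the information, 0.0154 at both looks, and the same R² in both arms. Adjustment would help with chance imbalance only in the covariates included.

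**What to change.** Before any unblinded interim look, amend SAP 8.1.2 so that the primary test is the arm coefficient from a linear model of total hypotension minutes on arm and a short, named covariate list:

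- age;
- planned (not performed) type of surgery, with its levels defined;
- pre-induction MAP, provided that a baseline window is defined and the value can be retrieved from the monitor record in both arms.

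Use a heteroscedasticity-robust standard error, since the SAP itself assumes unequal SDs, and the same α′ at both looks. State a simple rule for missing baselines, such as the overall mean plus a missing indicator. Keep the unadjusted t-test as supportive.

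The documents do not say whether the interim has taken place. If it has been unblinded, leave the primary test alone and add the adjusted model to SAP 8.1.3 as a supportive analysis.

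The cost is SAP wording, one model, and the work of defining the covariates and MAP window in advance. It needs no new patients or visits; baseline MAP may need to be extracted from existing monitor files.

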8.1.3. Sensitivity Analysis

The objective of sensitivity analysis is to guarantee the robustness of the statistical analysis conclusion drawn from statistical hypothesis test. Following sensitivity analyses are designed in this study:

- A. Modification of hypotension definition:
 - A1. The effectiveness of the threshold of MAP on statistical conclusion, check the analytical conclusion sensitivity to changes of the MAP threshold value to define hypotension instance from 50 mmHg to 70 mmHg with step=5 mmHg.
 - A2. The time length cut off used in hypotension instance definition, check the analytical conclusion sensitivity to changes of the cut off time length from 20 seconds to 80 seconds with step=20 seconds.
- B. The effectiveness of sample size:
 - B1. With bootstrap method, draw analytical conclusion by analysis based on the sub-set of study data sampled from the whole study data, check the consistency between the whole data analysis result and the simulated sub-dataset analysis result.
 - B2. Including the study subject with missing covariate information or cohort structure in the analytical dataset, check the consistency between the analysis with all study subject and on the analysis result with FAS subject.

8.1.4. Interim Analysis

To monitor the effectiveness and safety of HPI software on hypotension management in cardiac surgery and ICU for study patient requiring cardiac pulmonary bypass, one interim analysis is planned and will be conducted at the time that half of the enrolled study subjects' complete surgery and the hemodynamic measurements are downloaded from the monitoring platform.

To compensate for the early look at the data during the interim analysis, using the Pocock methodology, for this study design, 11~12% extra study subjects will be enrolled. Considering drop-out through withdraw ICF, lost follow-up, and roll-in subjects for training et al, another 10% attrition is added for subject enrollment, considering the study subject randomization, the final sample size is 175 subjects per group.

This interim analysis focuses on the primary effectiveness endpoint, the subject total hypotension duration during post-cardiac pulmonary bypass stage and the first 8 hours for patients in intensive care unit. The reduction of mean hypotension duration between the HPI arm and control group will be tested by t (student) statistics with $n_1 + n_2 - 2$ degree of freedom. If the corresponding p value of this t statistics is less than the critical p value=0.0154 (the type I error allocation by the study design) together with the mean hypotension

 Edwards	Revision Date: May 7, 2024	Rev	For Use Only by Affiliates of Edwards Lifesciences	Page 16
	Title	A randomized trial of the Hypotension Prediction Index in the cardiac operating room and the intensive care unit		

minutes of HPI arm study subject is smaller than the number of control group study subject, the null hypothesis is rejected. By this interim analysis result, the study team will make a decision whether stop the clinical study or continue until the maximum study subjects are enrolled and the study is completed.

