The Modified intent-to-treat (mITT) population is composed of all subjects who pass the screen (inclusion/exclusion) evaluation, sign the informed consent form (ICF), are assigned a subject ID, and are randomized to a study group. This includes roll-in and pivotal subjects.

B. FAS population

FAS (full analysis set) population is composed of all pivotal subjects with valid HemoSphere observations.

C. PP population

The per protocol (PP) population is composed of all pivotal subjects without protocol deviations.

D. CC population

The complete cases (CC) population is composed of all the pivotal subjects who complete surgery and complete the trial.

Analysis Methods for the Primary Endpoint

The primary study objective is to evaluate if the use of HPI software in conjunction with a treatment protocol can statistically reduce the study patient's hypotension duration by the measurements taken in the cardiac OR and ICU, which has been shown to correlate with morbidity and mortality. By the hypotheses designed in sample size calculation, the following t statistics will be used to judge if the hypotension duration of the study arm with HPI software is statistically shorter or smaller than the control arm without HPI software.

$$t = \frac{\widehat{\mu}_1 - \widehat{\mu}_0}{\sqrt{S_p^2 \left(\frac{1}{n_1} + \frac{1}{n_0} \right)}}$$

Here $\widehat{\mu}_1, \widehat{\mu}_0$ is the mean hypotension duration estimation of the test arm and reference arm, respectively. The pooled variance, $S_p^2 = \frac{(n_1-1)*S_1^2 + (n_0-1)*S_0^2}{n_1+n_0-2}$, n_1, n_0 is the final valid subjects in test arm and reference arms respectively, S_1^2 and S_0^2 are the variance estimates of the test arm and reference arm respectively.

By the t statistics calculated with the data from clinical operation, compares to the critical t value ($t(\alpha', n_1 + n_2 - 2)$) to judge if null hypothesis is rejected. Here α' is the split type I error by study design for interim analysis and the final analysis, $n_1 + n_2 - 2$ is the degree of freedom.

For the interim analysis, by Pocock methodology with one-sided t test, $\alpha' = 0.015$. If p value deduces from the actual t value with $n_1 + n_2 - 2$ degrees of freedom is less than α' , H_0 will be rejected.

For the final analysis, using the Pocock methodology, with one-sided t test, $\alpha' = 0.015$. A similar computation will be done at the interim analysis.

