8.3. Multiplicity Adjustment

The family-wise Type I error rate between the primary efficacy and safety endpoints will be controlled using a hierarchical gatekeeping method. If the primary efficacy endpoint is not passed, then the safety endpoints will not be tested either. If the primary endpoint is passed, then the secondary endpoints will be tested using a one-sided α at the same level as the primary endpoint.

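### No pair of interim and final thresholds in the protocol or SAP holds the stated overall one-sided 0.025, and the SAP gives no number for the final analysis

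*Combined protocol and SAP*

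**What the plan says.** SAP 2.4.3 sets the design error: "type I error for this test is 0.025, test power=0.80". The accompanying table labels 0.025 as the overall one-sided alpha. SAP 8.1.4 states that "one interim analysis is planned and will be conducted at the time that half of the enrolled study subjects" have completed surgery and their data are downloaded, so there are two looks, the first at about half the information.

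The thresholds differ between the documents:

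- Protocol section 7 (Analysis Methods for the Primary Endpoint) sets 0.015 for the interim. It continues "For the final analysis, using the Pocock methodology, with one-sided t test", again at 0.015.
- SAP 8.1.2 and 8.1.4 reject at the interim if the p value "is less than the critical p value=0.0154 (the type I error allocation by the study design"). SAP 8.1.2 defines α′ as the type I error divided between interim and final, but gives it a value for the interim only.

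SAP section 1 says the SAP prevails where documents conflict. SAP section 10, on changes from the protocol, mentions only the SOFA score.

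For the secondary endpoints, SAP 8.3 says that once the primary passes they are tested one-sided "at the same level as the primary endpoint". SAP 8.4.1 gives 95% confidence intervals for the hypotension measures, and SAP 8.4.2 gives rates and differences for the clinical ones.

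**The concern.** The null hypothesis can be rejected at the interim, so error is spent there and the two thresholds must jointly add up to 0.025. The SAP changes the interim threshold from the protocol's value without giving a matching final value or recording the change. An analyst at the final analysis must therefore choose: borrow the protocol's 0.015, reuse 0.0154, or fall back on some other level. That choice should not be open once data have been seen in a confirmatory test.

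The same gap carries into SAP 8.3. The level that the secondary endpoints inherit is not a single defined number, and nothing says in what order they are tested or whether they are formally tested at all.

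**Working it through.** **Inputs (SAP 2.4.3 unless noted).** One-sided α = 0.025 and power 0.80. For the effect: "control group mean hypotension duration=29 minutes, its stand deviation=29.49, the expected reduction is 30"%, so the HPI mean is 0.70 × 29 = 20.3 and the difference is 8.7 minutes. For the HPI-arm SD, "the ratio between hypotension duration STD and mean is around 1.10", so 1.10 × 20.3 = 22.33. There are two looks at information fractions 0.5 and 1 (SAP 8.1.4), so the two test statistics have correlation √0.5 = 0.7071.

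**1. The plan's own sample size.** n per arm = (29.49² + 22.33²)(1.960 + 0.842)² / 8.7² = 1368.29 × 7.849 / 75.69 = 141.9, so 142. The SAP agrees: "The estimated subjects for each arm by 1:1 allocation is 142". The equal-boundary Pocock inflation factor at 80% power is 1.110, and 142 × 1.110 = 157.7, so 158. Then 158 / 0.9 = 175.6, against the stated 175. The sample size chain holds. The thresholds are where the plan departs from it.

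**2. Overall error for a pair (α₁, α₂).** With zᵢ = Φ⁻¹(1 − αᵢ) and Φ₂ the bivariate normal distribution function,

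overall α = 1 − Φ₂(z₁, z₂; ρ = 0.7071).

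| Interim | Final | Source of the pair | Overall one-sided α |
|---|---|---|---|
| 0.015 | 0.015 | protocol at both looks | 0.0255 |
| 0.0154 | 0.015 | SAP interim, protocol final | 0.0258 |
| 0.0154 | 0.0154 | SAP interim level reused | 0.0262 |

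A simulation of the pooled t-test (79 then 158 per arm, 400,000 runs) gives 0.0261 for the last row, so the normal approximation is adequate.

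**3. Equal-boundary Pocock.** Setting α₁ = α₂ and solving for an overall 0.025 gives z = 2.178, p = 0.01469 at each look.

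**4. Where 0.0154 may come from.** The Pocock-type spending function at fraction 0.5 gives 0.025 × ln(1 + (e − 1) × 0.5) = 0.025 × 0.6201 = 0.0155. The SAP's figure is close to this. Holding 0.0154 at the interim and solving for the final gives a maximum of 0.01397. Rounded down, 0.0154/0.0139 gives an overall 0.0249. Rounded up to 0.0140 it gives 0.02502.

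**5. Power at 157 per arm** (175 × 0.9 = 157.5). The drift at the final is 8.7 / √(1368.29 / 157) = 2.947, and at the interim 2.947 × 0.7071 = 2.084.

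| Pair | Power |
|---|---|
| 0.0154 / 0.0154 | 80.4% |
| 0.0147 / 0.0147 | 79.9% |
| 0.0154 / 0.0139 | 79.4% |

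**6. Secondary endpoints.** SAP 8.4.1 lists 4 time-weighted averages and 4 MAP thresholds × 4 periods = 16 durations. SAP 8.4.2 lists 3 clinical endpoints. The total is 4 + 16 + 3 = 23. SAP 8.3 gives no order, split or adjustment among them. SAP 8.4.1 and 8.4.2 name no test or p value for any of them.

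**The case against.** The best defence is that the numbers are nearly right. The protocol's 0.015 is 0.0147 rounded to three decimals, an overall excess of 0.0005. The SAP's 0.0154 is not an error in itself: 0.0147 is unique only for equal boundaries, and the SAP's language of splitting and allocating the error fits a spending approach. The SAP overrides the protocol only in a conflict, and silence is arguably not a conflict, so the protocol's final 0.015 may still stand. All of this is fair. It limits the size of the problem but does not remove it, because 0.0154 followed by 0.015 still gives 0.0258, and no document states the lower final level that 0.0154 requires.

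Two stronger readings are tempting.

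- A reader might infer that the final will be tested at an unadjusted 0.025, the only other alpha that the SAP gives for the primary endpoint. That would give an overall 0.034. The documents do not support it: SAP 8.1.2 says the final uses a share of the divided error, and the protocol prints 0.015. It is a risk of misreading, not a stated rule.
- A reader might treat the secondaries as 23 free tests at 0.025 and compute 1 − 0.975²³ = 0.44, or a lower figure under correlation. This uses a level that the documents do not give for the primary at either look, and it ignores the gate in SAP 8.3. If nothing has an effect, a false secondary claim needs a false primary success first, so its chance cannot exceed the primary's own error. If the primary effect is real, the 23 nulls cannot all be true, since the primary is built from OR and CVICU time below 65 mmHg and both durations are themselves secondaries. Inflation among whichever secondaries are truly null remains possible, but its size has not been established.

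**Conclusion.** Wrong as written. The stated overall one-sided 0.025 is not delivered by any pair of thresholds in the documents. The actual level is 0.0255 to 0.0262, an excess of 0.0005 to 0.0012. That is numerically small. The more important defect is that the governing SAP has no numeric success criterion for the final analysis of its primary endpoint.

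These figures rest on an interim at exactly half the information and on approximate normality of the test statistics. A later or earlier interim shifts the valid levels: the equal-boundary level is 0.0144 at 45% of the information and 0.0150 at 55%.

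On the secondary endpoints the supported conclusion is narrower. SAP 8.3 announces formal tests at an undefined level with no order, SAP 8.4 describes only estimation, and the two must be reconciled.

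**What to change.** State one valid pair in SAP 8.1.2, SAP 8.1.4 and protocol section 7, before any unblinded data are seen:

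- equal-boundary Pocock, p = 0.01469 (z = 2.178, about 0.0147) at each look; or
- 0.0154 at the interim and 0.0139 at the final.

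Add that, if the interim does not fall at exactly half the information, the final level will be recomputed by the matching spending function. Record the change of threshold in SAP section 10.

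In SAP 8.3, name a short fixed sequence of secondary endpoints with a stated alpha, and label the rest descriptive, reported with confidence intervals only. Bring SAP 8.4.1 and 8.4.2 into line by giving the test for each endpoint in the sequence.

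The cost is a few numbers and one paragraph. Against 0.0154 at both looks, the first pair costs about 0.5 points of power and the second about 1 point. No additional subjects are needed if power of 79.9% or 79.4% at 157 per arm is accepted in place of the nominal 80%.
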